4.2 Scientific Rationale for Study Design

Rationale for enrolling pediatric participants

It is expected that infants who already had RSV infection or who are seropositive present a lower virus shedding and thus a lower probability of vaccine virus transmission to their close contacts (23). In VAD00014 study, potential pediatric participants will not be screened based on their RSV baseline serostatus. Therefore, in order to maximize the probability of transmission during the study, enrolling a higher proportion of children aged 6 to 12 months may help to increase the proportion of seronegative participants and thereby increase the probability of transmission to pediatric participants receiving the placebo and / or to ad-hoc close contact participants. Some efforts will be made to enroll twins, to optimize the probability of transmission, and to limit the possible impact of age difference between the RSVt vaccine and placebo recipients. Stratification by age group could also be a way to control for the age distribution among RSVt vaccine and placebo recipients (eg, to ensure that for siblings, some younger and older children will receive RSVt vaccine).

Evaluation of Vaccine Virus Transmission

Transmission of the vaccine virus will be defined as presence of detected vaccine virus in the pediatric participants placebo-recipients and ad-hoc close contact participants, by RSVt qRT-PCR assay. Planned nasal swabs will be collected on all pediatric participants (ie, vaccinees and placebo recipients) on D01, D04, D08, D11, D15, D18, D22, D64, and D71. Nasal swabs will not be collected on D57 or D85 since vaccine virus shedding is not expected to last so long after the first administration and is expected to be lower after the second administration.

Based on an NIH study conducted with the same vaccine construct and on the same target population (20), it is expected that the probability of transmission from vaccinees to other persons will be higher when the virus shedding in the vaccinees is the highest (between 4 and 9 days after vaccine administration), so that nasal swabs will be collected regularly after the first administration to be able to detect vaccine virus. Vaccine virus shedding is expected to be lower after the second administration (8), justifying the collection of fewer nasal swabs after the second administration, and performing the interim analysis of the primary objective of transmission after the first dose.

[REDACTED]

Illness Visit(s)

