5.1 Inclusion Criteria

5.1.1 Inclusion Criteria

Participants are eligible for the study only if all of the following criteria are met:

AGE

I01. Aged 6 months to < 24 months on the day of inclusion¹

TYPE OF PARTICIPANT AND DISEASE CHARACTERISTICS

I02. Participants who are healthy as determined by medical evaluation including medical history.

I03. Born at full term of pregnancy (≥ 37 weeks) or born after a gestation period of 27 through 36 weeks and medically stable as assessed by the investigator, based on the following definition: “Medically stable” refers to the condition of premature infants who do not require significant medical support or ongoing management for debilitating disease and who have demonstrated a clinical course of sustained recovery by the time they receive the first dose of study intervention

I04. Attends a daycare facility at least 3 days per week and 4 hours per day at which the participant would be in a contact group/playroom of at least one other child 6 to < 24 months of age who will participate in this study or is a member of a household, which includes at least one other child 6 to < 24 months of age who will participate in this study

INFORMED CONSENT

I05. Informed consent form has been signed and dated by the parent(s) or other legally acceptable representative (and by an independent witness if required by local regulations)

OTHER INCLUSIONS

I06. Participant and parent/legally acceptable representative are able to attend all scheduled visits and to comply with all study procedures

¹ “6 months to < 24 months” means from the day of the 6 months after birth to the day before the 2nd birthday

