E08. Attends a daycare facility and shares a daycare room with infants less than 6 months of age, and parent/legally acceptable representative is unable or unwilling to suspend attendance at the daycare facility for 28 days following study intervention administration

E09. Any need of supplemental oxygen therapy in a home or hospital setting at the time of enrollment.

PRIOR/CONCOMITANT THERAPY

E10. Participant's mother previous receipt or planned administration of an investigational RSV vaccine or any monoclonal antibody (such as Infliximab) during pregnancy and/or breastfeeding.

E11. Receipt or planned receipt of any of the following vaccines prior to or after the first study intervention administration:

- any influenza vaccine within 7 days prior to and after, or
- any COVID-19 or inactivated vaccine or live-attenuated rotavirus vaccine within 14 days prior to and after, or
- any live vaccine, other than rotavirus vaccine, within 28 days prior to and after

E12. Previous receipt of an investigational RSV vaccine or receiving any anti-RSV product (such as ribavirin or RSV IG or RSV monoclonal antibody) at the time of enrollment.

E13. Receipt of immune globulins, blood or blood-derived products in the past 3 months

E14. Receipt of intranasal and intra-ocular medications within 3 days prior to study enrollment

E15. Receipt at the time of enrollment or previous receipt of salicylate (aspirin) or salicylate-containing products

PRIOR/CONCURRENT CLINICAL STUDY EXPERIENCE

E16. Participation at the time of study enrollment (or in the 6 weeks preceding the first study intervention administration) or planned participation during the present study period in another clinical study investigating a vaccine, drug, medical device, or medical procedure

OTHER EXCLUSIONS

E17. Deprived of freedom in an emergency setting, or hospitalized involuntarily

E18. Identified as a natural or adopted child of the Investigator or employee with direct involvement in the proposed study

If the participant has a primary physician who is not the investigator, the site should contact this physician with the participant's consent to inform him / her of the participant's participation in the study. In addition, the site should ask this primary physician to verify exclusion criteria relating to previous therapies, such as receipt of blood products or previous vaccines.

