9.5 Sample Size Determination

No sample size calculation was done as there are no statistical hypotheses in this study. A total of 100 pediatric participants (ie, 50 per study intervention group) are planned to be enrolled, based on clinical feasibility.

10 Supporting Documentation and Operational Considerations

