### 3.2 Sample Size Determination

No sample size calculation was done as there are no statistical hypotheses in this study. A total of 100 pediatric participants (ie, 50 per study intervention group) are planned to be enrolled, based on clinical feasibility.

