### 3.3 Populations for Analyses

For the purposes of analysis, the following analysis sets are defined:

Participant Analysis Set	Description
Randomized	Pediatric participants for whom a study intervention group has been allocated.
Safety Analysis Set (SafAS)	Pediatric participants who have received at least one study intervention administration. All pediatric participants will have their safety analyzed after each vaccination according to the study intervention they actually received, and after any vaccination according to the study intervention received at the first study intervention administration.  Safety data recorded for a vaccine received out of the protocol design will be excluded from the analysis (and listed separately).
Full Analysis Set (FAS)	Subset of randomized pediatric participants who received at least one study intervention administration.  Pediatric participants will be analyzed according to the study intervention to which they were randomized.

Per-protocol analysis set (PPAS)	
The PPAS is a subset of the FAS.
 
The pediatric participants presenting with at least one of the following relevant protocol deviations will be excluded from the PPAS:
 

• Pediatric participant did not meet all protocol-specified inclusion criteria or met at least one of the protocol-specified exclusion criteria

• Pediatric participant did not receive first study intervention administration at D01

• Pediatric participant received a study intervention at D01 other than the one that he / she was randomized to receive

• Preparation and / or administration of study intervention at D01 not done as per-protocol

• Pediatric participant NOT having at least 4 nasal swabs (with a valid result) between D08 and D22, with a maximum of 5 days' time interval between 2 consecutive nasal swabs

• Pediatric participant received a protocol-prohibited therapy before collection of nasal swab between D08 and D22

• Pediatric participant with an emergency unblinding performed by the investigator before collection of nasal swab at D22

• Pediatric participant who was RSV- exposed before study intervention administration at D01

Other analysis set	An analysis set will be used to document transmission of vaccine virus in the ad-hoc close contact participants

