**Table 3.1: Descriptive statistics produced**

Disposition and follow-up description	Categorical data	Number of participants. Percentage of participants.
	Continuous data	Mean, standard deviation, quartiles, minimum, and maximum.
Baseline characteristics	Categorical data	Number of participants. Percentage of participants.
	Continuous data	Mean, standard deviation, quartiles, minimum and maximum.
Clinical safety results	Categorical data	Solicited: Number and percentage (95% CIs) of participants. Unsolicited: Number and percentage (95% CIs) of participants and number of events.
Vaccine virus shedding results	Categorical data	Number and percentage (95% CIs) of participants.
	Continuous data	Mean and standard deviation, quartiles, minimum, and maximum.
Transmissibility results	Categorical data	Number and percentage (95% CIs) of participants.
Vaccine virus stability	Categorical data	Number and percentage (95% CIs) of participants.
Immunogenicity results	Categorical data (cutoff)	Number and percentage (95% CIs) of participants.
	Continuous data (titer / data)	Log10: Mean and standard deviation. Anti-Log10 (work on Log10 distribution, and anti-Log10 applied): Geometric mean, 95% CI of the geometric mean, quartiles, minimum, and maximum. Graphical representation by Reverse Cumulative Distribution Curve (RCDC)
Infectivity results	Categorical data	Number and percentage (95% CIs) of participants.
RSV WT infection	Categorical data	Number and percentage (95% CIs) of participants, number of events, and 95% CI.

The statistical methodology will be based on the use of two-sided 95% confidence intervals (CI).

All endpoints will be summarized by study intervention group. For the main parameters, 95% CI of point estimates will be calculated using the normal approximation for quantitative data and using the exact binomial distribution (Clopper-Pearson method) for proportions.

For immunogenicity data, assuming that Log10 transformation of the titers/titers ratio follows a normal distribution, at first, the mean and the 95% CI will be calculated on Log10 (titers/titers ratio) using the usual calculation for normal distribution (using Student's t distribution with n-1 degree of freedom), then antilog transformations will be applied to the results of calculations, in

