### 3.4.2 Primary Endpoints

#### 3.4.2.1 Vaccine virus transmission

Presence of vaccine virus detected by RSVt qRT-PCR ( $\geq$ LOD) in nasal swabs after the first vaccination (D01, D04, D08, D11, D15, D18, and D22) will be summarized in pediatric participants receiving placebo with 95% CIs:

- Number and percentage of participants with vaccine virus detected at each timepoint
- Number and percentage of participants with vaccine virus detected in at least one nasal swab

Transmissibility analyses will be performed on the SafAS and PPAS. Vaccine virus transmission is defined in [Section 4.2.1](#).

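### The transmission denominators set no condition on contact with a vaccinee, while I04 and E08 together can admit daycare children kept apart for the whole primary swab period

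*Protocol*

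**What the plan says.** **Entry.** Protocol 5.1.1, I04, has two routes: a household with another participating child, or daycare contact. The daycare route begins "Attends a daycare facility at least 3 days per week and 4 hours per day" and requires another participant in the same contact group or playroom. Protocol 5.2, E08, applies to a child who shares a daycare room with infants under 6 months, and excludes that child only where the parent is "unable or unwilling to suspend attendance at the daycare facility for 28 days following study intervention administration". The suspension is implied as a condition of entry; it is not set out as a study procedure.

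**Endpoint.** Under SAP 3.4.2.1, detection of vaccine virus in the D01, D04, D08, D11, D15, D18 and D22 swabs "will be summarized in pediatric participants receiving placebo with 95% CIs", on the SafAS and PPAS. Protocol 4.2 expects transmission to be most likely when shedding in the vaccinee is highest, "between 4 and 9 days after vaccine administration".

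**Analysis sets.** Under SAP 3.3 the SafAS requires one administration. The PPAS exclusions concern the child's own eligibility, dosing, swabs (for example "at least 4 nasal swabs (with a valid result) between D08 and D22"), prohibited therapy, unblinding and prior RSV exposure. SAP 4.2.6.3 defines RSV-exposed by baseline anti-F IgA, that is, past infection rather than contact with a vaccinee. The transmission definition in SAP 4.2.1 has no contact condition. The Schedule of Activities lists no item on daycare attendance.

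**Size and method.** Protocol 9.5: "A total of 100 pediatric participants (ie, 50 per study intervention group) are planned to be enrolled, based on clinical feasibility". SAP 3.2: "No sample size calculation was done as there are no statistical hypotheses in this study". Intervals are computed "using the exact binomial distribution (Clopper-Pearson method) for proportions" (SAP 3.4.1).

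**The concern.** Protocol 4.1 enrols children in settings chosen to make transmission as likely as possible. For a child who qualifies only through a daycare room covered by E08, the condition of entry removes that contact. Every participant from such a room falls under the same criterion, so the group would not meet at daycare during the suspension.

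There is a second possible route to no exposure: a contact group without an RSVt recipient. Randomization is stratified by contact group and age group (SAP Table 1.1), but neither document states a block size or a rule that each group must contain a vaccinee.

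A placebo child without contact cannot acquire vaccine virus from a participant, yet stays in the denominator as a negative. The error runs one way, towards a lower rate and a lower upper limit. That is the less cautious direction for a study meant to show that a large trial can be run safely, with interim results going to health authorities before Phase III (SAP 3.5).

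**Working it through.** **1. The plan's own figure.** 100 × 1/2 = 50 placebo children, as stated. There is no power or precision calculation to reproduce.

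**2. Timing.** The suspension covers 28 days after administration, so D01 to D29. Days from dose to each primary swab (visit day minus 1) are 0, 3, 7, 10, 14, 17 and 21, or at most 22 with the +1 day window. All are within 28, as are days 4 to 9 of highest shedding. If E08 applies to each administration, D64 and D71 (7 and 14 days after D57) are inside as well.

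**3. Dilution.** Let u be the number of unexposed among 50 placebo children. The documents do not give u, so 0 to 25 is an assumed range. If unexposed children have no chance of a positive swab, the expected reported rate is the true rate × (50 − u)/50. With no positives, the Clopper-Pearson upper limit is 1 − 0.025^(1/n), and the chance of at least one positive at a true 5% rate is 1 − 0.95^n, with n = 50 − u.

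| u | n | A true 10% reads as | Upper limit for 0/n | P(at least 1 positive), true 5% |
|---|---|---|---|---|
| 0 | 50 | 10% | 7.1% | 92.3% |
| 5 | 45 | 9% | 7.9% | 90.1% |
| 10 | 40 | 8% | 8.8% | 87.1% |
| 20 | 30 | 6% | 11.6% | 78.5% |
| 25 | 25 | 5% | 13.7% | 72.3% |

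With no positives, the plan would report 7.1% in every row. With 5 positives, 5/50 = 10.0% (95% CI 3.3 to 21.8), against 5/40 = 12.5% (4.2 to 26.8) if 10 were unexposed.

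**4. Models in SAP Appendix 2.** Take 5 positives, 10 of 50 placebo children unexposed, and one vaccinee in every other group.
- *Unexposed through suspension, I_j = 1.* Both models count the 10 children and give 5/50 = 0.100 instead of 5/40 = 0.125.
- *Unexposed because the group has no vaccinee, I_j = 0.* The Reed-Frost contribution with X_j = 0 is q^0 = 1, so these groups drop out and the estimate is 0.125. The Greenwood estimate is ΣX_j/ΣS_j, which keeps them: 5/50 = 0.100.

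**5. Groups without a vaccinee.** If contact group and age group are crossed strata, a mixed-age pair is two strata of one child. Under independent 1:1 assignment (an assumption, as the block size is not stated), both receive placebo with probability 1/2 × 1/2 = 1/4. This shows that the route is possible, not that it will be used.

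**The case against.** **How many children.** E08 concerns only daycare rooms shared with infants under 6 months. Recruitment favours twins and siblings, and E08 does not separate children who live together. A suspended child with an enrolled sibling is still exposed. Stratification by contact group and enrolment in pairs or small groups make placebo-only groups less likely. All of this stands: the number may be small or zero, and the larger values in the table are illustrations.

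**The PPAS.** It drops children who fail an inclusion criterion. A child kept home, with no household route, could be said not to meet I04 and so to leave the PPAS. That reading is available, but I04 is assessed at inclusion and neither document adopts it. A reader might infer that the PPAS certainly keeps these children; the text does not settle that either. The SafAS keeps them on any reading.

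**The estimand.** The objective is descriptive and concerns placebo recipients. The rate in all dosed placebo children is a legitimate summary, and transmission given contact is a different quantity. A set that depends on attendance after randomization should not simply replace the planned result. This stands, and it is why the exposed set belongs beside the SafAS and PPAS.

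**Dose-2 timing.** Visit 8 has a window of +7 days. If first doses fell on the same day, a placebo child dosed 7 days after the source would have the D64 and D71 swabs 14 and 21 days after the source's dose. A reader might infer that these swabs miss the shedding peak. The documents do not support that. The peak is in the vaccinee, and a contact infected on source days 4 to 9 would be swabbed 14 − 9 = 5 to 14 − 4 = 10 days, and 21 − 9 = 12 to 21 − 4 = 17 days, after infection. The plan itself relies on dose-1 swabs up to D22.

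**Conclusion.** The concern holds in a limited form. I04 and E08 conflict for children who qualify only through a daycare room with infants under 6 months, and neither the SafAS nor the PPAS conditions on contact with a vaccinee. Any unexposed placebo child therefore biases the transmission percentage and its upper limit downwards.

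The direction follows from the definitions; the size is unknown. If 10 or 20 of 50 placebo children were unexposed, the zero-event upper limit among exposed children would be 8.8% or 11.6%, against a reported 7.1%. These figures assume the stated u and no exposure at all in those children. The documents do not support saying that unexposed children will be enrolled, only that the plan permits it and would not reveal it. No hypothesis or decision threshold depends on the limit. The point should be fixed, with moderate confidence.

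**What to change.** Reconcile I04 and E08, leaving the E08 safety rule unchanged, and say whether a suspended daycare child still meets I04 and stays in the PPAS. Then:

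- Record in the CRF whether daycare was suspended, with dates.
- Before unblinding, define an exposed-placebo set: at least one RSVt recipient in the same contact group, and either household contact or no daycare suspension during D01 to D22 by the placebo child or by the only source. For dose 2, apply the same condition from the second dose to the D71 swab. The contact-group identifier is already part of the participant number (Protocol 6.3.1).
- Report dose-1 and dose-2 transmission on this set beside the planned SafAS and PPAS results, and state the number unexposed.
- Exclude no-contact groups and groups with I_j = 0 from the Greenwood likelihood, and suspended groups without household contact from both models.

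The cost is SAP wording and one CRF field with dates. The exposed set will have a smaller denominator and a slightly wider interval.

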5.3 Lifestyle Considerations

No other restrictions than the ones listed in the exclusion criteria or in the contraindications for subsequent vaccinations are required.

5.4 Screen Failures

A screen failure occurs when a participant who consents to participate in the clinical study is not subsequently randomly assigned to study intervention. Screening information is recorded in the source documents.

Individuals who do not meet the criteria for participation in this study (screen failure) can be rescreened.

5.5 Criteria for Temporarily Delaying Enrollment/Randomization/Administration of Study Intervention

The Sponsor may decide to temporarily delay the enrollment/randomization/administration of study intervention in case of occurrence of an event requiring further investigation and until the Sponsor's governance decision on further steps.

Temporary intervention discontinuation may be considered by the investigator because of suspected AEs or disruption of the clinical trial due to a regional or national emergency declared by a governmental agency. For all temporary intervention discontinuations, duration should be recorded by the investigator in the source documents.

6 Study Interventions and Concomitant Therapy

Study intervention is defined as any investigational intervention(s), marketed product(s), placebo, or medical device(s) intended to be administered to a study participant according to the study protocol.

Note: Vaccines or products administered outside of study protocol are not considered as study interventions and are reported in the CRF as reportable medications (see [Section 6.8](#)). Study procedures (eg, blood sampling) are also not considered as study interventions.

6.1 Study Interventions Administered

Study interventions are described in [Table 6.1](#).

Table 6.1: Study Interventions Administered

Intervention Name	RSVt Vaccine [REDACTED]	Placebo
Use	Experimental	Placebo
IMP and NIMP	IMP	IMP
Type	Vaccine	Vaccine
Dose Form	Nasal spray suspension	Nasal spray suspension
Unit Dose Strength	Each [REDACTED] dose of RSVt vaccine will contain the live-attenuated RSV with [REDACTED] [REDACTED] [REDACTED] dose.	Same formulation buffer as RSVt vaccine
Excipients/Diluent	[REDACTED] [REDACTED] [REDACTED]	Same formulation buffer as RSVt vaccine
Dosage Level(s)	[REDACTED]	[REDACTED]
Number of Doses / Dosing Interval	2 doses 56 days apart for pediatric participants	2 doses 56 days apart for pediatric participants
Route of Administration	Intranasal	Intranasal

Site of Administration	Each nostril	Each nostril
Sourcing	Provided by the Sponsor	Provided by the Sponsor
Packaging and Labeling	The investigational and placebo products in single-dose vials will be supplied with investigational labeling and packaging according to national regulations. Each single dose of investigational or placebo product will be identified by a unique number on the primary label and on the outer carton label. The carton label will also have a detachable label for the sites to attach to the source documents.	
Current/Former Name(s) or Alias(es)	Not applicable	Not applicable
Batch Number	TBD	TBD
Storage Conditions	Study interventions will be stored in a freezer at $\leq -60^{\circ}\text{C}$ ($\leq -76^{\circ}\text{F}$) and will be protected from the light.	

IMP: Investigational Medicinal Product; NIMP: Non-Investigational Medicinal Product; TBD: to be determined

Table 6.2 summarizes the study interventions per arm.

Table 6.2: Study Arms

Arm title	Group 1 RSVt	Group 2 Control
Arm type	Experimental	Placebo
Associated study interventions	RSVt vaccine	Placebo

